11. ADMINISTRATIVE MATTERS

To comply with ICH Guideline for GCP or other applicable guidelines (such as GEP and GVP) administrative obligations relating to data collection, monitoring, archiving data, audits, confidentiality, ownership and publications must be met.

Anticipated study milestones are presented below. Any changes to those initial milestones will be reported in the study report:

Milestone	Planned date	Actual date*	Comments
Approval by Ethics Committees	28 September 2018	24 August 2018	Approval of the protocol
First subject enrolled	01 October 2018	N/A	First visit anticipated
Last subject enrolled	15 January 2019	N/A	Last visit anticipated
Database Freeze	22 March 2019	N/A	None
Completion of Statistical Analysis	19 April 2019	N/A	None
Final Report of Main Study Results	06 June 2019	N/A	None

**to be completed at the date of the final study report*

11.1. Case Report Form/Electronic Case Report Form Instructions

A validated GSK defined electronic data collection tool will be used as the method for data collection.

In all cases, subject initials will not be collected nor transmitted to GSK. Subject data necessary for analysis and reporting will be entered/transmitted into a validated database or data system. Clinical data management will be performed in accordance with applicable GSK standards and data cleaning procedures.

While completed eCRFs are reviewed by a GSK Biologicals' Site Monitor at the study site, omissions or inconsistencies detected by subsequent eCRF review may necessitate clarification or correction of omissions or inconsistencies with documentation and approval by the investigator or appropriately qualified designee. In all cases, the investigator remains accountable for the study data.

Once the database is archived and the clinical study report is complete and approved by all parties, each participating investigator will be provided with a CD-ROM of the final version of the data generated at his/her investigational site.

11.2. Study Monitoring by GSK Biologicals

GSK will monitor the study to verify that, amongst others, the:

- Data are authentic, accurate, and complete.
- Safety and rights of subjects are being protected.
- Study is conducted in accordance with the currently approved protocol, any other study agreements, GCP and all applicable regulatory requirements.

The investigator and the head of the medical institution (where applicable) agrees to allow the monitor direct access to all relevant documents.

The investigator must ensure provision of reasonable time, space and qualified personnel for monitoring visits.

Direct access to all study-site related and source data is mandatory for the purpose of monitoring review. The monitor will perform an eCRF review and a Source Document Verification (SDV)/Source Document Review (SDR) per Risk Based Monitoring Plan. By SDV we understand verifying eCRF entries by comparing them with the source data that will be made available by the investigator for this purpose.

The Source Documentation Agreement Form describes the source data for the different data in the eCRF. This document should be completed and signed by the site monitor and investigator and should be filed in the monitor's and investigator's study file. Any data item for which the eCRF will serve as the source must be identified, agreed and documented in the source documentation agreement form.

For eCRF, the monitor will mark completed and approved screens at each visit.

Upon completion or premature discontinuation of the study, the monitor will conduct site closure activities with the investigator or site staff, as appropriate, in accordance with applicable regulations, GCP, and GSK procedures.

11.3. Record Retention

Following closure of the study, the investigator must maintain all site study records (except for those required by local regulations to be maintained elsewhere) in a safe and secure location. The records must be easily accessible, when needed (e.g., audit or inspection), and must be available for review in conjunction with assessment of the facility, supporting systems, and staff. Where permitted by applicable laws/regulations or institutional policy, some or all of these records can be maintained in a validated format other than hard copy (e.g., microfiche, scanned, electronic); however, caution needs to be exercised before such action is taken. The investigator must ensure that all reproductions are legible and are a true and accurate copy of the original and meet accessibility and retrieval standards, including re-generating a hard copy, if required. Furthermore, the investigator must ensure that an acceptable back-up of the reproductions exists and that there is an acceptable quality control procedure in place for making these reproductions.

GSK will inform the investigator/institution of the time period for retaining these records to comply with all applicable regulatory requirements. However, the investigator/institution should seek the written approval of the sponsor before proceeding with the disposal of these records. The minimum retention time will meet the strictest standard applicable to a particular site, as dictated by ICH GCP or other applicable guidelines, any institutional requirements or applicable laws or regulations, or GSK standards/procedures; otherwise, the minimum retention period will default to **30** years.

The investigator/institution must notify GSK of any changes in the archival arrangements, including, but not limited to, archival at an off-site facility and transfer of ownership of the records in the event the investigator leaves the site.

11.4. Quality Assurance

To ensure compliance with GCP, GEP, GVP, or other applicable guidelines and all applicable regulatory requirements, GSK may conduct a quality assurance audit. Regulatory agencies may also conduct a regulatory inspection of this study. Such audits/inspections can occur at any time during or after completion of the study. If an audit or inspection occurs, the investigator and institution agree to allow the auditor/inspector direct access to all relevant documents and to allocate his/her time and the time of his/her staff to the auditor/inspector to discuss findings and any relevant issues.

11.5. Posting of Information on Publicly Available Registers and Publication Policy

GSK assures that the key design elements of this protocol will be posted on the GSK website and in publicly accessible database(s) such as clinicaltrials.gov, in compliance with the current regulations.

GSK also assures that results of this study will be posted on the GSK website and in publicly accessible regulatory registry(ies) within the required time-frame, in compliance with the current regulations.

11.6. Provision of Study Results to Investigators

Where required by applicable regulatory requirements, an investigator signatory will be identified for the approval of the study report. The investigator will be provided reasonable access to statistical tables, figures, and relevant reports and will have the opportunity to review the complete study results at a GSK Biologicals site or other mutually-agreed location.

GSK Biologicals will also provide the investigator with the full summary of the study results. The investigator is encouraged to share the summary results with the study subjects, as appropriate.

11.7. Data Sharing

Under the framework of the SHARE initiative, results of GSK studies may be combined with non- GSK studies, to investigate further about the study product(s) and other product(s), and /or the disease/condition under investigation and related diseases and conditions.

12. COUNTRY SPECIFIC REQUIREMENTS

There are no country-specific requirements for Belgium or Spain and one for Germany related to gender distribution.

Explanatory statement concerning Gender Distribution (Article 7, paragraph 2 (12) of the German GCP ORDER)

The EPI-FLU-056 study does not involve administration of an investigational product. GSK's quadrivalent seasonal influenza vaccine is approved for active immunization of persons aged 6 months and older for the prevention of disease caused by influenza A subtype viruses and type B viruses contained in the vaccine and will be administered according to routine medical practice prior to subject's enrolment in the study. As per inclusion criteria, both females and males are eligible to be part of the study with no specific restrictions associated with gender. The objective of the study is to assess AEs or other AEs experienced within 7 days post vaccination regardless of gender.

There is no intent to analyse the safety of GSK's quadrivalent seasonal influenza vaccine by gender which implies that the potential relationship between the gender distribution and the safety outcomes will not be under scrutiny in this enhanced safety surveillance.


CONFIDENTIAL Subject Number: -

Enhanced safety surveillance of GSK's quadrivalent seasonal influenza vaccine

Symptoms or reactions you experienced in the 7 days (i.e., the day of vaccination and the following 6 days) after your influenza vaccination	Please tick if you experienced the symptom	Start date of the symptom dd/mm/yyyy
Irritated or red eyes		__/__/__
Runny nose		__/__/__
Blocked nose		__/__/__
Nose bleed		__/__/__
Common cold		__/__/__
Cough		__/__/__
Sore throat		__/__/__
Hoarse voice		__/__/__
Wheezing		__/__/__
Loss of appetite		__/__/__
Nausea – feeling sick to your stomach		__/__/__
Vomiting – being sick to your stomach		__/__/__
Diarrhoea		__/__/__
Fever (temperature >38°C)		__/__/__
Allergic reaction (rash, itchy skin and/or eyes, runny nose)		__/__/__
Severe allergic reaction (Rash, difficulty breathing, dizziness, fast heart rate, swelling of lips/tongue)		__/__/__
Swelling of the face		__/__/__
Rash in a restricted part of the body		__/__/__
Rash all over body		__/__/__
Feeling irritable		__/__/__
Feeling tired		__/__/__
Headache		__/__/__
Shivering or feeling shaky		__/__/__
Seizure / fits		__/__/__
Muscle aches		__/__/__
Joint pain		__/__/__
Redness around injection site		__/__/__
Swelling around injection site		__/__/__
Pain at the injection site		__/__/__
Other		
1. _____		__/__/__
2. _____		__/__/__
3. _____		__/__/__

APPENDIX B Code list of pre-specified AEs

Project title: Passive enhanced safety surveillance of GSK's quadrivalent seasonal influenza vaccines: a pilot study in Belgium, Germany and Spain during the 2018/19 influenza season

Preferred code list

If a patient presents with adverse events within 7 days following vaccination (i.e., the day of vaccination and the following 6 days), please code (ideally as a **symptom**) any of the following events into their computerised record

Pre-defined Adverse Events of Interest	MedDRA PT Terms	ICD-10 Codes	Notes
Respiratory/Miscellaneous			
Conjunctivitis	Conjunctivitis (10010741)	H10.9	Irritated or red eyes
Rhinorrhoea	Rhinorrhoea (10039101)	J34.89	Runny nose
Nasal congestion	Nasal congestion (10028735)	R09.81	Blocked nose
Epistaxis	Epistaxis (10015090)	R04.0	Nose bleed
Coryza	Rhinitis (10039083)	J00	Common cold
Cough	Cough (10011224)	R05	Cough
Oropharyngeal pain	Oropharyngeal pain (10068319)	J02.9	Sore throat
Hoarseness	Dysphonia (10013952)	R49.0	Hoarse voice
Wheezing	Wheezing (10047924)	R06.2	Wheezing
Gastrointestinal			
Decreased appetite	Decreased appetite (10061428)	R63.0	Loss of appetite
Nausea	Nausea (10028813)	R11.0	Feeling sick
Vomiting	Vomiting (10047700)	R11.10	Being sick
Diarrhoea	Diarrhoea (10012735)	R19.7	Diarrhea
Fever/pyrexia			
Fever	Pyrexia (10037660)	R50.9	Temperature >38°C
Sensitivity/anaphylaxis			
Hypersensitivity reaction	Hypersensitivity (10020751)	T78.4	Allergic reaction
Anaphylactic reaction	Anaphylactic reaction (10002198)	T78.2	Severe allergic reaction
Facial oedema	Face oedema (10016029)	R60.0	Swelling of the face
Rash			
Rash	Rash (10037844)	L27.1	Rash in a restricted part of the body
Generalised rash	Rash generalised (10037858)	L27.0	Rash all over body

Pre-defined AEs	MedDRA PT Terms	ICD-10 Codes	Notes
General non-specific symptoms			
Irritability	Irritability (10022998)	R68.12 (Fussy baby) R45.4 (Irritability and anger)	Feeling irritable
Fatigue	Fatigue (10016256)		Feeling tired
Headache	Headache (10019211)	R51	Headache
Neurological			
Bell's palsy	Facial paralysis (10016062)	G51.0	
Peripheral tremor	Chills (10008531)	R68.83	Shivering/chills
Guillain-Barré Syndrome (GBS)	Guillain-Barre syndrome (10018767)	G61.0	
Seizure/ Febrile convulsions	Febrile convulsion (10016284)	R56.0	Seizure/fits
Musculoskeletal			
Muscle aches/ myalgia	Myalgia (10028411)	M79.1	Muscle aches
Arthropathy	Arthropathy (10003285)	M25.9, M19.9	Joint pain
Local Symptoms			
Local erythema	Injection site erythema (10022061)	T50.895	Redness around the injection site
Local swelling	Injection site swelling (10053425)	T50.895	Swelling around the injection site
Local pain	Injection site pain (10022086)	T50.895	Pain at the injection site
If a patient hands back the ADR card with their symptoms – please code these and include the code XXXX			

N.B.: In coding these conditions there is no assumption about causation; this can only come from advanced analytics.

Principal Investigator: XXXX

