2.1. Risk Assessment

Important Potential Risks	Data/Rationale for Risk	Mitigation Strategy
Anaphylaxis	Anaphylaxis can occur at any age, with the highest age-specific rates observed in the 0-19 year group (70 cases per 100,000 person-years). Anaphylaxis following immunisation is serious but rare; the estimated incidences are in the range of 1-10 per 1 million doses distributed depending on the vaccine distributed [Ruggeberg, 2007].	The investigator/prescribers are advised of possible anaphylaxis following GSK's quadrivalent seasonal influenza vaccine administration by information included in product labels.

Important Potential Risks	Data/Rationale for Risk	Mitigation Strategy
Febrile seizure	
In April 2010, there was a reported increase in febrile convulsion following influenza vaccination in young children in Western Australia. Following extensive investigations into this safety issue, epidemiological analyses determined that administration of the 2010 seasonal influenza vaccines, Fluvax® and Fluvax Junior® (manufactured by Bio CSL), was associated with an increased risk of febrile convulsions, however, the risk has not been confirmed for other influenza vaccines, including GSK's quadrivalent seasonal influenza vaccine.
	
As with other vaccines, vaccination with GSK's quadrivalent seasonal influenza vaccine should be postponed in subjects suffering from an acute febrile illness; fever is also listed as an adverse reaction.

Guillain-Barré syndrome (GBS)	
A few cases of GBS have been reported to GSK. Most published studies investigating GBS suggest incidence estimates between 0.84 and 1.91 per 100,000 persons per year. To date, a total of 29 published studies investigating GBS have been carried out in ten European countries. The majority of studies (21/29) provided an incidence estimate that fell between 1.0 and 2.0 per 100,000 persons per year. [McGrogan, 2009].
	
None: GBS is listed as rare adverse reaction in the label. There is no known prevention for GBS.

Bell's palsy	
The annual incidence of Bell's palsy is 15 to 30 per 100,000 people. The peak incidence occurs between the second and fourth decades (15 to 45 years). 10% of patients experience one or more recurrences [Greco, 2012]. Bell's palsy has been reported in people who had intranasal influenza vaccine. A link between Bell's palsy and seasonal influenza vaccine that are given by intramuscular injection has not been established.
	
None

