7.4.7. ADR cards

Customized ADR cards will be used to collect the AEs and/or other AEs within 7 days post each vaccination (i.e., the day of vaccination and the following 6 days). After written informed consent/informed assent is obtained from the subject/the subject’s parent(s)/LAR, the ADR cards will be provided to the subjects/subjects’ parent’(s)/LAR on the day of vaccination. The subjects/subjects’ parent’(s)/LAR will be asked to complete the ADR cards with any AEs and/or other AEs occurring within 7 days post vaccination and to return the cards to the HCP at the next study visit or by mail. The investigator or delegate will transcribe the collected information into the eCRF database.

Note: ADR cards can be filled in by a minor subject under the supervision of the subject’s parent(s)/LAR(s) provided that the minor has the competence to assess and report the information to be provided on the ADR cards. The ultimate accountability for the completion of the ADR cards remains with the subject’s parent(s)/LAR(s). The investigator should discuss this accountability with the subject’s parent(s)/LAR(s).

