8.1.2. Definition of a serious adverse event

An SAE is any untoward medical occurrence that:

- a. Results in death,
- b. Is life-threatening,

Note: The term 'life-threatening' in the definition of 'serious' refers to an event in which the subject was at risk of death at the time of the event. It does not refer to an event, which hypothetically might have caused death, had it been more severe.

- c. Requires hospitalisation or prolongation of an existing hospitalisation,

Note: In general, hospitalisation signifies that the subject has been admitted at the hospital or emergency ward for observation and/or treatment that would not have been appropriate in the physician's office or in an out-patient setting.

Complications that occur during hospitalisation are also considered AEs. If a complication prolongs hospitalisation or fulfils any other serious criteria, the event will also be considered serious. When in doubt as to whether 'hospitalisation' occurred or was necessary, the AE should be considered serious.

Hospitalisation for elective treatment of a pre-existing condition (known or diagnosed prior to informed consent signature) that did not worsen from baseline is NOT considered an SAE.

- d. Results in disability/incapacity,

Note: The term disability means a substantial disruption of a person's ability to conduct normal life functions. This definition is not intended to include experiences of relatively minor medical significance such as uncomplicated headache, nausea, vomiting, diarrhoea, influenza like illness, and accidental trauma (e.g., sprained ankle) which may interfere or prevent everyday life functions but do not constitute a substantial disruption.

or

- e. Is a congenital anomaly/birth defect in the offspring of a study subject.

Medical or scientific judgement should be exercised in deciding whether reporting is appropriate in other situations, such as important medical events that may not be immediately life-threatening or result in death or hospitalisation but may jeopardise the subject or may require medical or surgical intervention to prevent one of the other outcomes listed in the above definition. These should also be considered serious. Examples of such events are invasive or malignant cancers, intensive treatment in an emergency room or at home for allergic bronchospasm, blood dyscrasias or convulsions that do not result in hospitalisation.

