8.1.3. Adverse events of specific interest

AEs that comprise the primary interest of the study are designated as AEs. Please refer to [APPENDIX C](#) for the pre-defined list of AEs.

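### Appendix B gives the card item for any seizure only the narrower Preferred Term for febrile convulsion, a named important potential risk

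*Protocol*

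**What the plan says.** The ADR card (Appendix A) has a tick box and start date for seizure or fits, with no condition on fever. Fever is its own item, "Fever (temperature >38°C", with its own box and date.

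In Appendix B, under the neurological heading, the adverse event of interest (AEI) is "Seizure/ Febrile convulsions", the note repeats the card's lay wording, and the only PT is "Febrile convulsion (10016284". No other seizure PT appears in the list.

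Appendix B asks the practice to code "any of the following events into their computerised record" and closes by asking that symptoms on a returned card be coded. Section 7.4.7 describes the route for the study data: the investigator or a delegate "will transcribe the collected information into the eCRF database". Sections 10.6, 10.7 and 10.10.2 tabulate the card data by MedDRA PT and do not say which list supplies the PTs. Section 8.1.3 sends the reader to Appendix C "for the pre-defined list of AEs", but Appendix C is the amendment log, so Appendix B is the only AEI-to-PT list in the protocol.

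Section 2.1 lists febrile seizure among the important potential risks. It describes an increase in young children after another manufacturer's vaccine and says that "the risk has not been confirmed for other influenza vaccines", this one included.

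**The concern.** The PT is narrower than the question put to the subject. A tick beside pre-printed text gives a coder nothing more to work from, and the one PT the protocol offers for that tick presupposes fever. Applied as written, the list would put a seizure without fever into the row of a named important potential risk and so show a case of that risk that did not occur.

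This could happen in adults too. Section 5.2 restricts Belgium and Germany to subjects aged 18 or over, and German sites aim mainly at those aged 50 or over. An afebrile seizure in an older adult would be read as an event that the risk table discusses for young children.

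**Working it through.** **1. Breadth of the terms, side by side**

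| Place | Term | Fever required? |
|---|---|---|
| ADR card | Seizure / fits | No |
| ADR card, separate item | Fever above 38°C | Not linked to the seizure item |
| Appendix B, AEI name | "Seizure/ Febrile convulsions" | Not for the first half of the name |
| Appendix B, note | Seizure/fits | No |
| Appendix B, only PT | "Febrile convulsion (10016284" | Yes |

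The mismatch follows from the protocol's own words.

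**2. Link from the list to the tables.** It is inferred. In its favour: the list has a PT column, its notes follow the card's lay wording, it ends with an instruction to code returned cards, and it is the only such list. Against: it names the patient's computerised record as the target, whereas the analysis data reach the eCRF by transcription.

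**3. Size.** The documents give no seizure frequency, so I assume one afebrile seizure. The denominators are the planning figures in Tables 4 and 5: 1000 overall, 333 per country and 25 per country-week.

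Exact (Clopper–Pearson) 95% limits:
- x = 0: lower 0; upper 1 − 0.025^(1/n).
- x = 1: lower 1 − 0.975^(1/n); upper is the p that solves (1 − p)^n + n·p·(1 − p)^(n−1) = 0.025.

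The plan's own figures come first. For n = 1000 and a true 0.1%, the chance of at least one event is 1 − 0.999^1000 = 63.2%, and the limits for 1/1000 are 0.00–0.56%. Both agree with Table 4.

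| Denominator | Row as coded (1 event) | Row without the afebrile case (0 events) |
|---|---|---|
| 1000, overall | 0.10% (0.0025–0.556) | 0% (0–0.368) |
| 333, one country | 0.30% (0.0076–1.662) | 0% (0–1.102) |
| 25, one country-week | 4% (0.10–20.35, Table 4) | 0% (0–13.72, Table 5) |

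The last line is the scale of the weekly by-country tables, which the interim analyses also produce. In every line the total number of seizures is unchanged; only the label moves.

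**4. What else would show the true nature of the event.** Section 8.1.2 gives "convulsions that do not result in hospitalisation" as an example of a serious event. If the HCP judges the seizure related to the vaccine, Section 8.2 has it reported to the sponsor within 24 hours and Section 10.8 has it described in detail. If it is judged unrelated, no planned study output describes it, and the PT label carries the information alone.

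**The case against.** The strongest objection is that the consequence is not established. Appendix B is addressed to the practice's own records and its closing line still contains a placeholder code. The analysis sections never cite it. Central coding of the eCRF terms, or a coding plan not shown here, could assign a different PT. This stands, and it is why the effect is stated conditionally. The row itself remains narrower than the card item whatever coding is used.

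The slash in the AEI name may mark a synonym, as it does for muscle aches and myalgia; the AEI would then be febrile convulsion and the PT would match it. That reading is possible, but it does not remove the mismatch with the card, which is where the data come from.

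Other rows are also loosely mapped, for instance irritated or red eyes to conjunctivitis and joint pain to arthropathy. This is true. The seizure row differs in that its PT coincides with a named important potential risk.

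All analyses are descriptive, no threshold depends on the row, the investigator reviews the data, and the fever tick and dates are kept. This stands and limits the weight of the point.

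Finally, splitting on a self-reported fever tick could move a true febrile seizure with unticked fever out of the risk row. That is a fair warning, and it is why the fix includes a listing of every seizure.

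**Conclusion.** The concern holds as a minor point. Appendix B assigns a PT that presupposes fever to a card item that does not. If the list feeds the PT tables, one afebrile seizure would turn the febrile convulsion row from 0/1000 into 1/1000 overall, and from 0/333 into 1/333 in the country concerned.

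This rests on two assumptions: that Appendix B supplies the table PTs, which is likely but not stated, and that at least one afebrile seizure is ticked on a card. If either fails, the tables are unaffected. The seizure is counted in any case, and one judged vaccine-related would normally be described separately as a serious event. The exposed case is an afebrile seizure judged unrelated.

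**What to change.** - In Appendix B, map the card's seizure item to a general seizure PT, with name and code checked in MedDRA.
- Keep febrile convulsion for seizures with documented fever, for example where the card's fever item is ticked with a compatible start date. Write down the date rule before coding begins.
- Add a listing of every reported seizure with fever tick, both start dates and age, so that a febrile seizure with unticked fever stays visible.
- If other coding feeds the tables, say so in the protocol and still align the row with the card.

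The main cost is one row in the code list and one short listing from items already collected. No HCP confirmation step and no new data collection are needed.
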